8.2 Health Service Use Tracer condition populations

Subset of populations in section 8.1, excluding those without a tracer condition (asthma, constipation, or eczema).

Definition of tracer condition: Uses the same methodology applied by the CYPHP call/recall system, i.e. diagnosis, disease management, or therapy codes in the primary care record, and age restrictions. The clinical (Read/SNOMED) codes and therapies are listed in Appendix. For all conditions, an individual's complete records are interrogated.

If a subject meets the call/recall criteria for a tracer condition, they are defined as having a tracer condition from the first recorded event used in the definition (e.g. if they are defined as having asthma due to having an asthma diagnosis or three prescriptions of asthma medication in one year, we define their asthma 'start date' as the date of the first of those prescriptions or diagnosis).

We treat all conditions as ongoing, i.e. the observation period is continuous from the 'start date' of their condition (described above) until their observation 'end date' which occurs when they leave a GP practice, turn 16 years of age, or reach the end of the study period.

➤ Randomised HSU Tracer condition population

Intervention and control only, *excluding* pilot clusters

Subpopulations:

- Asthma
- Eczema
- Constipation

➤ Quasi-experimental HSU Tracer condition population

Intervention, control *and* pilot clusters

Subpopulations:

- Asthma
- Eczema
- Constipation

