4.2 CYPHP Evelina London model (intervention arm)

In addition to the components of the EUC arm, the CYPHP Evelina London model comprises two types of clinical services:

Targeted care for CYP with ongoing (tracer) conditions

CYP with tracer conditions are eligible for a tailored clinical service delivered by the multidisciplinary CYPHP Health team in primary and community care settings and in patients' homes. Children are actively identified for the service using a call and recall system which interrogates their primary health care records for evidence of the condition from diagnosis, management or treatment, identifies CYP with a tracer condition, and invites the parent/carer to complete a CYPHP Health Check. Health Check responses are used to triage CYP based on clinical need. The length and intensity of intervention is left to the clinical judgement of the multi-disciplinary team delivering CYPHP services.

Universal care available for CYP with any condition.

CYP with any condition are eligible for “in-reach” CYPHP clinics. These clinics are integrated child health clinics jointly run by GPs and local “Patch Paediatricians” who are linked to a cluster of GP practices. Clinics are held in primary care settings. They offer generalist and specialist advice co-located and coordinated conveniently close to home for patients. In-reach clinics will typically be for CYP who would otherwise have been referred to hospital for an outpatient appointment with a general paediatrician.

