8. STUDY POPULATIONS

8.1 Health Service Use Population level populations

Inclusion criteria:

- Aged 0-15 (<16) years
 - Within the study period (April 2018 to June 2020)
- Registered with a randomised Southwark or Lambeth GP practice
 - Within the study period (April 2018 to June 2020)

This will be an open cohort, including children who register with a GP practice during the course of the trial. Trial arm assignment is described in section 18.

Exclusion criteria:

We excluded children who had <30 days observation time. Reasons for short observation time include

- Children turning 16 years shortly after the start of the trial period,
- Children registering with a GP practice shortly before the end of the trial period.

➤ Randomised population

Intervention and control only, *excluding* pilot clusters or practices where the randomisation allocation could not be determined.

➤ Quasi-experimental population

Intervention, control *and* pilot clusters

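### Tracer service-use membership (SAP 8.2) can rest on codes recorded after allocation; if coding differs by arm, rates could differ with no true effect

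*SAP*

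**What the plan says.** Section 8.2 takes the tracer definition from the service's own case-finding tool: "Uses the same methodology applied by the CYPHP call/recall system", meaning diagnosis, management or therapy codes in the GP record, with age limits. On the window it says "For all conditions, an individual's complete records are interrogated". No date restricts which codes count. The worked example for asthma is "having an asthma diagnosis or three prescriptions of asthma medication in one year". On entry, children who meet the criteria "they are defined as having a tracer condition from the first recorded event used in the definition", so a child who qualifies at a third prescription is counted from the first of the three. On exit, "We treat all conditions as ongoing" until the child leaves the practice, turns 16 or reaches the end of the study period.

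The parent population in section 8.1 is open: "This will be an open cohort, including children who register with a GP practice during the course of the trial". Section 7.1 puts trial start at 1 April 2018 and adds that implementation began in some areas during the 2017/18 set-up year.

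Section 4.2 gives two components to intervention practices only. One is for tracer conditions: "CYP with tracer conditions are eligible for a tailored clinical service delivered by the multidisciplinary CYPHP Health team". The other is joint GP and paediatrician in-reach clinics, held in primary care, for children with any condition. Decision support, the paediatric hotline and the Health Check, whose information is added to GP records, are in both arms (section 4.1).

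The section 10.9 model adjusts for age, sex, deprivation and borough, and for cluster-level factors including the baseline rate. It has no term for disease severity or time since onset.

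**The concern.** A subgroup of a randomised population keeps the protection of randomisation only if membership is settled before allocation or cannot be influenced by it. Section 8.2 secures neither. A child with no tracer code on 1 April 2018 can join the tracer analysis on codes written during the trial, when the arms are receiving different care. Running one algorithm in both arms does not help if treatment alters the algorithm's inputs.

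The SAP gives some reason to expect such a change. Its hypothesis in section 1.1 is better quality of care in intervention practices. Several indicators in section 9.4 (spacer prescribing, macrogols, emollients, topical steroids, asthma review) are therapy or management records, the broad categories that section 8.2 uses for membership. Section 10.3.4 allows for extra referrals from the discovery of unmet need.

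At stake are the section 8.2 service-use rates and the three condition subgroups, including the condition-specific tertiary referral and attendance outcomes in sections 10.3.3 and 10.5.3. If one arm's denominator gains children with a different underlying rate, the rate ratio moves although no child's use of services has changed. No analysis restricted to children coded before the trial is planned against which to check this.

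**Working it through.** **1. Which routes could make coding differ by arm?**

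- *Call/recall to the tailored service (4.2).* The tool finds the child first, then comes the Health Check, triage and any service. A child arriving this way already meets the definition, so later codes cannot add that child to the any-tracer population or change the start date. They could add a second condition and so affect a condition subgroup.
- *In-reach clinics (4.2).* Intervention only, and not dependent on an existing tracer code. They could lead to new codes.
- *Improved primary care (1.1, 9.4).* If it occurs as hypothesised, it could change therapy and management coding.
- *Health Check, decision support and hotline (4.1).* Both arms, so no direct reason for a difference.

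A difference by arm is plausible but not stated. The code lists are in a spreadsheet that is not shown.

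**2. Mixture calculation with no true effect.** The SAP gives no event or coding rates for this population, so every input in steps 2 and 3 is an assumption. Let fc and fi be the shares of tracer person-time from newly coded children in control and intervention, and r their event rate relative to other tracer children.

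RR = (1 − fi + fi·r) / (1 − fc + fc·r)

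Example with fc = 0.10, fi = 0.25, r = 0.5: (0.75 + 0.125)/(0.90 + 0.05) = 0.875/0.95 = 0.921.

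| r | fi = 0.10 | fi = 0.15 | fi = 0.20 | fi = 0.25 |
|---|---|---|---|---|
| 0.3 | 1.000 | 0.962 | 0.925 | 0.887 |
| 0.5 | 1.000 | 0.974 | 0.947 | 0.921 |
| 0.8 | 1.000 | 0.990 | 0.980 | 0.969 |
| 1.0 | 1.000 | 1.000 | 1.000 | 1.000 |
| 1.5 | 1.000 | 1.024 | 1.048 | 1.071 |

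(fc = 0.10 throughout.) The ratio is exactly 1 when fi = fc or r = 1, and the sign turns on r.

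**3. Simulation of the three-prescriptions-in-a-year rule, no true effect.** Assumptions: 400,000 children per arm; gamma severity with mean 1; 1.5 contacts and 0.05 admissions per year, each multiplied by severity and identical in both arms; two years of prior record; 3.25 trial years (1 April 2018 to 30 June 2021, the section 7.1 period; section 8.1 gives June 2020, and the two need reconciling). Expected admissions were used to limit sampling noise. The chance that a contact yields a qualifying prescription was 0.30 for everyone before the trial and for control during it; only the in-trial intervention value varied.

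| Intervention chance | Tracer person-time ratio, as written | Admission RR, as written | Admission RR, entry at qualifying date | Admission RR, membership fixed before start |
|---|---|---|---|---|
| 0.30 | 0.998 | 1.000 | 1.000 | 0.999 |
| 0.40 | 1.262 | 0.944 | 0.952 | 1.004 |
| 0.50 | 1.527 | 0.893 | 0.906 | 0.999 |

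Consultation ratios as written were 1.000, 0.971 and 0.933; with membership fixed before start they were 0.997, 1.006 and 1.001.

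**4. What drives the bias.** With equal coding, backdating gives 1.000. With unequal coding, removing it moves 0.944 to 0.952 and 0.893 to 0.906, about one percentage point. The rest comes from who is admitted to the population, and only fixing membership before the trial removes that.

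**The case against.** The strongest reply is that the plan's own pathway runs the other way. Call/recall identifies the child and the service follows, so the tailored service cannot create the membership of children it received through that tool. The SAP nowhere says that the intervention team writes codes into the GP system; the one stated route into those records, the Health Check, is open to both arms. This stands. A reader might infer that the intervention itself generates the qualifying codes, but that goes further than the document. What remains is in-reach clinics, second conditions and improved primary care, which may change coding.

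A reader might also infer that extra children would be milder, so that the error favours the intervention. The SAP does not support a direction. In-reach clinics are typically for children who would otherwise go to hospital outpatients, which does not suggest mild disease, and r = 1.5 puts the ratio above 1.

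The backdated entry date is another tempting culprit. It does count time on the strength of later events, but step 4 shows that it contributes little between arms.

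Finally, fixing membership in advance alters the question, because call/recall defines who may be offered the service and that group changes over time. This is fair, and is why the all-records population should be kept as a secondary analysis. It does not justify leaving the randomised comparison without a version that allocation cannot influence.

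**Conclusion.** The risk is real but conditional. Section 8.2 allows post-allocation codes to determine membership, the planned covariates do not measure the risk difference that would matter, and no planned analysis would reveal the problem. Bias arises only if coding differs by arm and the newly coded children differ in risk. Under the assumed inputs the rate ratio with no effect runs from about 0.89 to 1.07. For scale, the population design in section 5.1 targets a 20% reduction in non-elective admissions. The lowest values need large imbalances: the simulated 0.893 came with 53% more tracer person-time in the intervention arm, which a report of new coding by arm should make visible.

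It would be wrong to read this as touching the trial's primary results or every tracer analysis. The all-children admission comparison (8.1) does not use tracer status. The section 8.3 population is set by Health Check completion and threshold. The consented populations (8.4, 8.5) rest on consent and accept self-reported conditions. This is a cheap improvement to a secondary comparison.

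**What to change.** - For the randomised section 8.2 comparison and its subgroups, define membership from call/recall criteria met on records dated before 1 April 2018, or before cohort entry if later.
- Add a sensitivity analysis with the cut-off at 31 March 2017, because section 7.1 says implementation began in some areas during 2017/18.
- Keep the all-records definition as a secondary analysis, starting person-time on the date the criteria are met rather than at the first prescription. That date change alone is not a cure.
- Report the number and rate of newly coded tracer cases by arm, overall and by condition.

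The cost is SAP wording and a date rule applied to records already being extracted. The downside is that incident cases and children born during the trial appear only in the secondary analysis, so the main tracer sample is smaller, by an amount the SAP does not allow us to state, and describes children with prevalent conditions.

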8.3 HSU Tracer condition population where Health Check shows clinical need

Purpose: Study impact of intervention on health service use of CYP meeting criteria for CYPHP clinical service

Inclusion criteria:

- Completed a Health Check, and Health Check results meet or exceed threshold for clinical need (see Appendix for thresholds).
- Aged 0-15 (<16) years
 - At time of completing a health check
- Registered with a randomised Southwark or Lambeth GP practice
 - At time of completing a health check

For health service use events, include only those which occur within 12 months after Health Check completion.

➤ Randomised HSU Tracer condition in clinical need population

Intervention and control only, *excluding* pilot clusters

Subpopulations:

- Asthma
- Eczema
- Constipation

➤ Quasi-experimental HSU Tracer condition in clinical need population

Intervention, control *and* pilot clusters

Subpopulations:

- Asthma
- Eczema
- Constipation

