5.2 Recruitment

The CYPHP Evelina London model of care is part of a service quality improvement initiative by a local partnership including service providers and commissioners of care, and is being implemented after extensive consultation and co-development with local stakeholders. Therefore, and in keeping with guidelines for the ethical conduct of cRCT's, patients within GP practices are being asked for their consent to participate in the follow-up evaluation, rather than consent for participation in a new model of care as this is part of a new standard service roll out. (Campbell et al, 2012)

OVERVIEW OF RECRUITMENT – TRACER CONDITION

- 1) **Providing service information for CYP and families.** Eligible patients with one of the three tracer conditions will be identified by their GP and receive text messages and a letter and information sheet outlining the new services being delivered in their GP practice. Potential participants are invited to contact the service, either by telephone or by logging onto a web page. The web page is a portal modelled on an existing and well-established platform in use for several years by another local programme (IMPARTS). It was adapted for use in CYPHP and tested for acceptability with local CYP and families.
- 2) **Inviting CYP and parents to participate in evaluation.** Parents of CYP receiving the service (either the CYPHP Evelina London model or EUC) for a tracer condition will be invited to participate in the evaluation, and provided with information sheets about the evaluation, in formats for the parent and child. These will be provided through the portal, in person, or by post.

3) **Informed consent/assent.** Those who would like to participate will be asked to give informed consent (using the web-based portal, in person, or by post) to participate in the evaluation and follow-up. Specifically, parents will be asked to:

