- provide informed consent for the evaluation team to 1) access their child's clinical details including a baseline clinical screening questionnaire which is completed on entry into the clinical service, and 2) have access to, and link, the child's GP and hospital data to assess the impact of CYPHP on both primary and secondary health service use. The baseline clinical screening questionnaire, completed for clinical services, includes the Strengths and Difficulties Questionnaire, and a condition-specific questionnaire: Asthma Control Test, GSTT Symptom Severity Measure (for constipation), or Patient Oriented Eczema Measure.
- complete an evaluation questionnaire at baseline (including health related quality of life measured by PEDSQL and CHU9D, and parental wellbeing measured by the Warwick-Edinburgh Mental Wellbeing Scale), and complete the clinical screening questionnaire and evaluation questionnaire at 6-month, and annual follow-up.
- give informed consent to be contacted to potentially participate in qualitative studies evaluating the service

Patient information sheets will make it clear that parents can consent or refuse consent to any of these components. Participants will be free to withdraw consent without prejudice at any time.

A parent/carer alone or with their child may be involved in the recruitment process. If the CYP is under 12 years of age the parent/carer will be asked to provide, on behalf of the child, informed consent, if they are happy to take part in the evaluation. If the CYP is between 12 and 16 years of age, the parent will be asked to provide informed consent and if the CYP is available at the time when parental consent is requested, the CYP will be asked to provide assent if they wish to participate.

TRACER CONDITION RECRUITMENT TIMELINE

Recruitment began in April 2018. The first participant was consented 22MAY2018, following their Health Check 24APR2018. Recruitment is planned to complete in December 2020.

POPULATION EVALUATION DATA

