5.4 Blinding

The study statistician, health economist, and researchers involved in recruitment will be blind to group allocation. The statistician and health economist will only have details of participants by study number and pseudonymised patient ID.

The evaluation will not be blinded at the level of the service delivery or participant.

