6.4 Survey/questionnaire data from study database

Once the patient has consented to the study the participants will be asked to complete further questionnaires (listed below). These are described in section **Error! Reference source not found.**

- PedsQL
- CHU9D
- WEMWBS
- School & Work Absence Questions
 - How many days of school has your child missed due to ill health or attending health-related appointments in the past three months?
 - How many days of work have you missed in the past three months due to your child's illness or healthcare appointments?

Follow-up data is collected at 6 and 12 months (+ up to 4 months) following baseline data collection. At the follow-up time points the Health Check questionnaires are also repeated.

The schedule of events for the tracer condition analysis of CYPHP is displayed in Table 1.

Table 1: Schedule of data collection for CYPHP Tracer Condition Questionnaires

	Procedures	CYPHP Health Check	Baseline Study Questionnaires	CYPHP Service entry	6-month Follow-up Study Questionnaires	12-month Follow-up Study Questionnaires
Health Checks	ACT	C			C	C
	POEM	C			C	C
	Constipation questionnaire	C			C	C
	SDQ	X			X	X
	Social Questions	X			X	X
	Health Check Demographics	X				
Evaluation Questionnaires	Eligibility assessment		X			
	Informed consent		X			
	PedsQL		X (1° child outcome)		X (1° child outcome)	X (1° child outcome)
	CHU9D		X		X	X
	WEMWBS		X (1° parent outcome)		X (1° parent outcome)	X (1° parent outcome)
	School & Work Absence Questions		X		X	X
CYPHP Services	Offer of CYPHP Services			Requires registration with GP in intervention arm and clinical need identified at Health Check triage		
	Receipt of CYPHP Services			Receive service if: Parent/carer/CYP agrees and takes up service		

X: collected on all participants

C: collected on participants with the relevant condition

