10.9 Health Service Use Analysis Methods

The population analyses will assess the effects of the CYPHP model on health service use for CYP with any (or no) health condition.

Main analysis: cRCT Intervention vs. control analysis

- Populations: See section 8
- Time period: See section 7
- Comparator: Study arm (Intervention vs Control)
- Endpoints: Rates of health service use (listed and defined in sections 9-10)
- Summary statistics: estimate of intervention effect, estimates of covariate coefficients, 95% confidence intervals, p-values

Formal analysis: Multi-level Poisson regression model

- Individual level covariates: age, sex, IMD 2015, IDACI 2015, Borough
- Cluster level covariates: IMD 2015, IDACI 2015, baseline rate of health service use endpoint, number of CYP under 16 per cluster, Rate of paediatric OP referrals 2015-16, Borough
- Data structure:
 - Individual data: Pt Identifier, Cluster, Study arm (Intervention/Control), Number of HSU events during observation period, Observation time (days), Rate of HSU events during trial, Age at baseline, Sex, IMD 2015, IDACI 2015, Borough of GP registration, Number of HSU events during baseline period, Length of baseline period (days), Baseline rate of HSU events
 - Cluster data: IMD 2015, IDACI 2015, baseline rate of health service use endpoint, number of CYP under 16 per cluster, Rate of paediatric OP referrals 2015-16, Borough

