23.5 Health Check Triage Thresholds

Participants with scores in the following ranges meet the symptom threshold to be offered CYPHP services (per the CYPHP Clinical Services Triage Document – August 2020 v 2.0):

- ACT 19 or below
- Constipation symptoms checklist score 3 or more
- POEM score 8 or more

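### The clinical-need service-use population (SAP 8.3) is selected after allocation on an unblinded Health Check, yet is labelled randomised and analysed without individual baseline use or entry severity

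*SAP*

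**What the plan says.** - **Entry (SAP 8.3).** A child enters on this condition: "Completed a Health Check, and Health Check results meet or exceed threshold for clinical need (see Appendix for thresholds". Outcomes are limited as follows: "For health service use events, include only those which occur within 12 months after Health Check completion". The version of this set without the pilot clusters is named as a randomised population.
- **Thresholds (SAP 23.5).** ACT 19 or below, constipation score 3 or more, POEM 8 or more, introduced by "Participants with scores in the following ranges meet the symptom threshold to be offered CYPHP services".
- **What families know (SAP 5.2, 5.4).** Before they respond, eligible patients "receive text messages and a letter and information sheet outlining the new services being delivered in their GP practice". On blinding: "The evaluation will not be blinded at the level of the service delivery or participant".
- **What the score leads to (SAP 6.4, Table 1).** The Health Check is offered in both arms (SAP 4.1), but the offer of CYPHP services "Requires registration with GP in intervention arm and clinical need identified at Health Check triage".
- **Model (SAP 10.9).** One multi-level Poisson model serves all section 8 populations. At the child level it has "Individual level covariates: age, sex, IMD 2015, IDACI 2015, Borough". At the cluster level it has IMD, IDACI, the baseline rate of the endpoint, number of children, outpatient referral rate and borough. Each child's own baseline event count, period and rate are in the data structure but not in the individual covariate line.
- **Contrast (SAP 11.9).** The questionnaire outcomes are adjusted for the individual baseline score.

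**The concern.** Randomising clusters balances the children registered in them. It does not balance a subset formed later by a family's decision to complete a questionnaire and by the answers given. Here the family can know which services its practice offers, and the consequence of a high score depends on the arm. Two things can then differ by arm: who completes the check, and how symptoms are reported. Either can shift the severity mix, and with it admission and ED rates, without any effect of the service.

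This is the service-use population closest to the targeted service, so readers will look there for an effect. The planned model has little to correct such a shift. Baseline use enters only as a cluster average, and no Health Check score enters at any level. I found no text that commits to reporting Health Check uptake, or the share over threshold, by arm.

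**Working it through.** The SAP gives no sample size, power or effect size for the 8.3 population, so there is no figure of its own to reproduce.

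**1. Does selection follow allocation?** The SAP does not date the randomisation. It gives the trial start as 1 April 2018 (7.1) and states: "The first participant was consented 22MAY2018, following their Health Check 24APR2018". The check is a service step and its onward offer depends on the arm, so it follows allocation by inference.

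**2. What does the model hold for an 8.3 child?**

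| Item | Available | In the 10.9 model |
|---|---|---|
| Cluster baseline rate of the endpoint | yes | yes |
| Child's own baseline event rate | yes, in the 10.9 data structure | not in the covariate line |
| ACT, POEM or constipation score | yes, it defines entry | no |
| SDQ total | collected at the Health Check | no |

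**3. Simple size, no true effect (assumed inputs).** Let severe children have twice the event rate of the others and make up a share p of an arm. The mean rate is proportional to 2p + (1 − p) = 1 + p.

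- p = 0.45 against 0.40: 1.45 / 1.40 = 1.036
- p = 0.50 against 0.40: 1.50 / 1.40 = 1.071

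Reversing the arms gives the inverse ratios.

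**4. Does score adjustment help?** A simulation with true rate ratio 1.00 used these assumed inputs: log-rate slope 0.3 or 0.6 per SD of severity, score reliability 0.8, and entry cut 0.3 SD above the mean. The rate ratio is intervention over control.

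| Mechanism | Strength | Slope | Without score | With score |
|---|---|---|---|---|
| Severity drives completion more in the intervention arm | extra log-odds 0.3 per SD | 0.3 | 1.021 | 1.009 |
| | | 0.6 | 1.045 | 1.017 |
| | extra log-odds 0.6 per SD | 0.3 | 1.034 | 1.015 |
| | | 0.6 | 1.070 | 1.026 |
| Intervention-arm parents report more symptoms at equal severity | 0.2 SD | 0.3 | 0.969 | 0.954 |
| | | 0.6 | 0.945 | 0.911 |
| | 0.4 SD | 0.3 | 0.942 | 0.908 |
| | | 0.6 | 0.895 | 0.827 |

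Under differential completion, adjustment removes a little over half of the bias: (1.070 − 1.026) / 0.070 = 63% in the largest case and (1.034 − 1.015) / 0.034 = 56% in the smallest. Under differential reporting it makes the bias larger. At an equal score the intervention child is truly milder, so conditioning on the score compares unlike children and exaggerates an apparent benefit.

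**5. Individual baseline rate.** The baseline years end on 31 March 2017 (7.1), before the set-up period, and come from records. They cannot be altered by how a parent later answers the Health Check. The simulation did not test this covariate. It controls measured imbalance in prior use but does not undo selection. Children born after 31 March 2017 have no baseline period and need explicit handling.

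**The case against.** **The bias is conditional.** The same Health Check and the same thresholds apply in both arms, and the researchers who recruit are blind to allocation. Nothing in the SAP shows that completion or scoring differs by arm. This stands: the documents support a risk, not a demonstrated bias.

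**Adjustment cannot restore randomisation.** This also stands. A reader might infer that adding the Health Check score cures the problem. Step 4 shows that it helps under one mechanism and harms under the other, so it belongs in a paired analysis.

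**Prior use is not wholly absent.** A reader might infer that the model contains nothing related to severity. It has the cluster-level baseline rate, and the child's own rate is already assembled. The gap is at the individual level.

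**The score may predict less than it seems.** A reader might take it as the best predictor of admissions. The SAP does not compare it with prior service use, and everyone in 8.3 has already crossed a threshold, which narrows its range.

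**The scores are awkward covariates.** The three condition scales differ. Constipation has 7 items for toilet-trained children and 5 for others. The SDQ total is not calculated when a subscale lacks three or more items. These are reasons for care in the specification; the entry score still exists for every member.

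**Some reporting may be planned.** Section 14.1 promises clinical baseline characteristics by arm, but its named variables include no condition score or SDQ. The return-rate reporting in section 21 is set out under consenting participants and questionnaires, and 8.3 does not require consent. The flow diagram and the outcome-by-population table are not available to me, so I claim nothing about their content.

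**Conclusion.** The point holds as one of labelling, covariates and reporting for a secondary population. The 8.3 set is formed by an unblinded, parent-completed check after allocation (inferred, as no randomisation date is given), and the result of that check has a different consequence in each arm. Calling it randomised overstates its standing, and the model leaves out individual baseline use that the SAP already assembles.

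The size is unknown. The ratios of 1.04 to 1.07, and the simulated range from about 0.83 to 1.07, rest wholly on assumed inputs. No 8.3 sample size is given against which to judge them.

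A reader might also infer that the trial's main result is compromised. It is not: the primary non-elective admission analysis in 8.1 and the record-defined tracer population in 8.2 do not depend on Health Check completion. The matter is minor but cheap to put right.

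**What to change.** For the 8.3 population, amend the SAP to:

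1. Add the child's own baseline event rate, already in the 10.9 data structure, as an individual covariate, with an indicator for children who have no baseline period.
2. Within each condition model, show the result with and without the entry ACT, POEM or constipation score (constipation by toilet-training status) and the SDQ total where it can be calculated. State beforehand that the score reduces bias from differential completion but can worsen bias from differential reporting.
3. Report by arm the share of eligible 8.2 tracer children who completed a Health Check, the share over threshold, and the distribution of scores.
4. Label the 8.3 result as non-randomised supportive evidence and present it beside the 8.2 result.

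The cost is SAP wording, some extra model runs and tables, and a rule for missing baseline data. No new data collection is needed. Fixing this before unblinding keeps the choice of adjustment from being made with the results in view.
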